### 9.3.5 Cardiac or Neurological Serious Adverse Events

If a cardiac or neurological SAE occurs within 48 hours of dosing, a blood sample (approximately 8 mL) will be collected as soon as possible for measurement of plasma bupivacaine CCI [REDACTED]. The collection date and time should be documented. Refer to the sample processing, shipping and handling instructions provided within the laboratory manual.

### 9.3.6 Adverse Event Follow-up

During and after participation by a patient in a clinical trial, the Investigator will ensure that adequate medical care has been provided to the patient for any AEs including clinically significant laboratory values related to the trial. The Investigator will inform the patient when medical care will be needed for intercurrent illness(es) of which Investigator becomes aware.

All AEs must be followed by the Investigator until resolution (no further changes in the event are expected, i.e., the point at which a subject experiencing such an AE has been appropriately

treated and stabilized even though they may continue to experience lingering sequelae that may never resolve), until the subject is lost to follow-up, or died and until all queries related to the AEs have been resolved. Investigators will make at least 3 documented attempts to contact a subject before considering the subject lost to follow-up. The first two attempts may be by letter, email or documented phone call and the third and final attempt must be by Registered Mail, Return Receipt Requested. If a subject dies during participation in the study or during a recognized follow-up period, the Sponsor (or designee) must be notified immediately and then provided with a copy of any post-mortem findings, including histopathology.

#### 9.4 Pregnancy

Female patients will be advised to notify the Investigator immediately if they become pregnant during the course of the trial.

The Investigator must complete the appropriate pregnancy reporting forms and send them to DURECT (or DURECT's designee) within 14 calendar days of obtaining information of the pregnancy. The Investigator will follow the pregnancy through its course and complete the appropriate documentation and forward immediately to DURECT (or DURECT's designee). The infant must be followed at least until one month of age. Consent of a parent must be obtained before registration of infant data.

Abortion, stillbirth and any malformation/disease must be reported as an SAE. A pregnancy outcome other than abortion, stillbirth and any malformation/disease as well as follow-up of the infant must be reported by the Investigator within 14 calendar days of obtaining the information using the appropriate pregnancy reporting forms.

#### 10.0 Pharmacokinetics

No PK assessments have been planned for this trial.

#### 11.0 Statistical Methods and Data Analysis

##### 11.1 Trial Design Considerations

###### Part 1

This part will be a randomized, parallel-group, double-blind, placebo-controlled, multi-center trial evaluating the safety and efficacy of SABER®-Bupivacaine 5 mL in patients undergoing elective outpatient laparoscopic cholecystectomy.

CCI

CCI [REDACTED]

Part 2

This part will be a randomized, parallel-group, double-blind, active-controlled, multi-center trial evaluating the safety and efficacy of SABER®-Bupivacaine 5 mL in patients undergoing elective outpatient laparoscopic cholecystectomy.

The primary efficacy objective will be to investigate whether SABER®-Bupivacaine will significantly reduce pain compared to bupivacaine HCl (75 mg) over 48 hours following test drug administration in patients undergoing laparoscopic cholecystectomy.

It has been planned that the data from centers that participate in this trial will be combined such that an adequate number of subjects will be available for analysis.

Unless otherwise specified, all statistical tests will be conducted employing a two-sided significance level of 0.05.

**11.2 Sample Size Determination**

Part 1

One hundred fifty three subjects enrolled in each treatment group of the study will result in 90% power (assuming type 1 error rate of 5%) to detect a difference between 5 mL of SABER®-Bupivacaine and 5 mL of saline placebo CCI [REDACTED]

[REDACTED] The size of the final enrollment will be approximately 90 subjects determined by the readiness of sites to enroll subjects under IRB-approved Part 2.

Part 2

One hundred thirty-two subjects enrolled in each treatment group of the study will result in 90% power (assuming type 1 error rate of 5%) to detect a difference between 5 mL of SABER®-Bupivacaine and 15 mL of 0.5% bupivacaine HCl CCI [REDACTED]

CCI

### 11.3 Patient Randomization

#### Part 1

It was planned that approximately 320 eligible patients would be randomized, in order to obtain 306 evaluable patients (i.e., patients who received any test drug and have at least one post-surgical pain intensity score). It had been estimated that 5% of randomized patients may not receive any test drug due to unforeseeable intra-operative exclusion. Patients would be randomized in a 1:1 ratio to receive one of two treatments based on a computer-generated randomization schedule prepared before the study:

- Treatment Group 1: SABER®-Bupivacaine 5 mL (132 mg/mL, 660 mg bupivacaine base)
- Treatment Group 2: Sterile normal saline 5 mL (0.9% sodium chloride injection, USP) (placebo)

Due to the early administrative stopping, only approximately 90 subjects will be enrolled and randomized in Part 1.

#### Part 2

Approximately 274 eligible patients will be randomized, in order to obtain 264 evaluable patients (i.e., patients who are randomized and received any test drug). It has been estimated that 4% of randomized patients may not receive any test drug due to unforeseeable intra-operative exclusion. Patients will be randomized in a 1:1 ratio to receive one of two treatments based on a computer-generated randomization schedule prepared before the study:

- Treatment Group 3: SABER®-Bupivacaine 5 mL (132 mg/mL, 660 mg bupivacaine base)
- Treatment Group 4: Bupivacaine HCl without epinephrine, 15 mL of 0.5% solution (75 mg)

For both Part 1 and 2, the randomization will be balanced by using randomly permuted blocks (block size of 4) and will be stratified by sex. The rationale for stratification by sex was differences in pain response reported in the literature for both acute/chronic pain ([Fillingim et al, 2009](#)), postoperative pain studies in cholecystectomy ([De Cosmo et al, 2008](#); [Uchiyama et al, 2006](#)) and a previous laparoscopic cholecystectomy trial (C803-025, Cohort 2) conducted by DURECT. [De Cosmo et al](#) found that females had a higher mean pain score ( $4.3 \pm 2.1$ ) than males ( $2.9 \pm 1.6$ ) during 24 hours postoperatively ( $p=0.003$  from repeated measure ANOVA). A significant sex effect on 24-hour postoperative pain was also reported by [Uchiyama et al](#).

If a given study center approaches randomization of 20% of the total number of evaluable subjects (264) into Part 2 of the trial, the Sponsor will assess the appropriateness of allowing the center to continue randomizing additional subjects into the trial based upon factors such as monitored site performance including documentation and protocol compliance. An IWRS system will be used to assign subjects to a treatment group.

If all Screening (i.e. pre-operative) Inclusion/Exclusion criteria are met, randomization can be done up to 1 business day prior to surgery. In the event that a randomized patient does not have the surgical procedure for unforeseen circumstances (such as conversion to open surgery, or the need to use more than 4 laparoscopic ports) or does not receive any test drug, replacement of the patient has been planned. IWRS system will be algorithmically instructed to issue the appropriate randomization replacement and to ensure the balance of treatment as planned. Precise details on the IWRS algorithm will be described in the IWRS specifications.

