14. Use of long-acting anticoagulants and antiplatelet drugs (with the exception of low dose aspirin [81 mg]) in the 1-week prior to surgery. (Short-acting new oral anticoagulants should be discontinued prior to surgery according to the label instructions.)

15. Patients who are incapable of operating the electronic diary (LogPad) and/or miss more than 1 of the practice diary assessments (i.e., are less than 80% compliant) during screening should not be randomized. Compliance with the LogPad assessments is essential to the study.
16. Patients who self-report an alcohol dehydrogenase deficiency.
17. Patients participating in any other trial with an investigational drug or device concurrently or less than 30 days prior to surgery for this trial.
18. Patients who, in the Investigator's opinion, should not participate in the trial or may not be capable of following the trial procedures for any reason.

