## 5.4 Trial Design

C803-028 is a randomized, parallel-group, double-blind, placebo-controlled (Part 1) and active-controlled (Part 2), multi-center trial evaluating the safety and efficacy of SABER®-Bupivacaine 5 mL in patients undergoing elective outpatient laparoscopic cholecystectomy.

[figure not shown]
The randomization will be stratified by sex (See [Section 11.3](#)). For Part 1, it was planned to enroll approximately 320 eligible patients (See [Section 5.3](#)) in a 1:1 ratio to receive one of two treatments: SABER®-Bupivacaine 5 mL; or sterile normal saline 5 mL (placebo) instilled directly into the laparoscopic ports at the close of surgery. The 5 mL of test drug is divided between the multiple ports to provide coverage of all surgical incisions (see [Section 7.3.1](#)). CCI

CCI  
[REDACTED] The data from Part 1 patients will continue to be blinded until the completion of Part 2 of the trial.

For Part 2 of the trial, 132 evaluable patients per treatment arm will provide at least 90% power (See [Section 11.2](#)) to meet the primary efficacy endpoint. In order to obtain 264 evaluable

patients, approximately 274 eligible patients (assuming 4% of patients may not be dosed due to unforeseeable intra-operative exclusion) will be randomized in a 1:1 ratio to receive one of two treatments: 5 mL of SABER®-Bupivacaine instilled directly into the laparoscopic ports or 15 mL of 0.5% bupivacaine HCl infiltrated into the port incisions at the close of surgery.

Five postoperative outpatient clinic visits will be scheduled for assessment of safety parameters including AEs and surgical site examinations and for collection of rescue medication usage data. All AEs, of whatever etiology and location, occurring after informed consent will be recorded on the eCRF. All AEs will be followed until resolution unless the patient is lost to follow up. Resolution means no further changes in the event would be expected, i.e., the point at which a subject experiencing such an AE is appropriately treated and stabilized even though they may continue to experience lingering sequelae that may never resolve.

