## 7.2 Maintenance of the Blind

For the best chance of achieving a valid and reliable test of efficacy, the blind must be maintained despite the fact that several members of the site staff (pharmacist, operating room staff) will necessarily be un-blinded by the difference in color and viscosity between SABER®-Bupivacaine and comparator (saline placebo [Part 1] or bupivacaine HCl [Part 2]) test drugs.

Nonetheless, un-blinded trial staff must not disclose which test drug the patient received, or bias the patient or blinded staff by discussing the group assignments with them. Surgeons and other operating room personnel should take care not to include any potentially unblinding information (e.g., volume or method of test drug administration) in their operative notes or other routinely collected surgical records). Assessment of study endpoints, such as adverse events and surgical site examinations, must be done by blinded personnel. During any routine postoperative clinical examinations, the un-blinded surgeon must take care not to inadvertently un-blind the patient. Any clinical examinations done by the operating surgeon will be done for standard of care only and must not be used for any of the trial-related surgical site examinations. Each site will have a site specific Blinding Plan in place to describe the steps taken to ensure the blind is maintained as well as indicating which study staff will be blinded or un-blinded. Included in this Blinding Plan will be a form that must be signed by the principal investigator stipulating that un-blinded staff have not discussed group assignment with blinded staff, and that all protocol related evaluations have been performed only by the latter.

Vial cartons will carry identical labels and vials will be packaged in individual cartons to avoid any side-by-side comparisons of the vial carton contents. Each vial carton and the boxes containing multiple vial cartons will have tamper-evident seals.

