### **7.3.6 Drug Accountability**

#### Test Drug

SABER®-Bupivacaine, saline placebo (Part 1) and bupivacaine HCl (Part 2) will be accounted for by the investigative site and recorded on the drug accountability log.

The test drug will be administered to the patient by the un-blinded surgeon; therefore no patient compliance measures with regard to the test drug are necessary. Additionally, specific test drug dosing information will be recorded on the appropriate source document and electronic case report form (eCRF).

All used syringes and needles will be disposed as per local health and safety standard operating procedures.

All used and unused test drug (SABER-Bupivacaine, saline placebo [Part 1], and bupivacaine HCl [Part 2]) vials will be kept at the investigative site until test drug reconciliation by the unblinded monitor and must be available for verification during monitoring visits.

After monitoring, a final reconciliation of drug accountability records, and authorization by DURECT, all used and unused vials of test drug will be returned to DURECT or properly disposed of at the investigative site, if permitted per local SOPs and regulations. Documentation of disposition of all test drug will be provided to DURECT.

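### Section 11.3 prints one fixed block size of 4 while un-blinded site staff see the assignments made at their site; varying and withholding it is a cheap safeguard against a probably small bias

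*Combined protocol and SAP*

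**What the plan says.** Section 11.3 sets the allocation method for both Parts: "the randomization will be balanced by using randomly permuted blocks (block size of 4) and will be stratified by sex". Part 2 is 1:1 between SABER-Bupivacaine and bupivacaine HCl, and the assigning tool is named: "An IWRS system will be used to assign subjects to a treatment group". Sex is the only stratification factor named (Sections 2.0, 5.4 and 11.3). Sections 7.1 and 11.3 leave the algorithm to the IWRS specifications, which are not among the documents, and part of Section 7.1 is redacted. Nothing visible says whether blocks are kept within a site or run across all sites.

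Patients and assessors are blinded, but the people who handle the drug are not. Section 7.2 accepts that "several members of the site staff (pharmacist, operating room staff) will necessarily be un-blinded by the difference in color and viscosity", and Section 7.3.6 adds: "The test drug will be administered to the patient by the un-blinded surgeon". Section 7.2 forbids these staff to reveal assignments to patients or blinded colleagues, and each site has a Blinding Plan. Under Appendix 6 the investigator reviews the protocol and keeps a copy in the site file.

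On entry, criterion 18 in Section 5.3.2 excludes anyone who, in the investigator's view, "should not participate in the trial or may not be capable of following the trial procedures for any reason". Randomization may take place up to one business day before surgery (Section 11.3). Section 6.1 allows 5 to 25 sites and provides for a sponsor review when a site nears 20% of the 264 evaluable patients. Patients who are randomized but not dosed are to be replaced (Sections 7.1 and 11.3).

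**The concern.** An IWRS stops anyone from reading the next assignment, but it does not stop them from inferring it from earlier ones. Someone who sees each arm at a site, and knows that every block holds two of each, can keep a tally by sex. If that person sees a whole block, two same-arm patients at its start reveal the other two.

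This matters only if that person can influence who is entered, or when. The visible text leaves room for it:

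- Section 7.4.2 describes a blinded investigator as someone other than the operating surgeon, which implies that an operating surgeon may also be an investigator.
- Section 5.6 makes suitability for randomization depend on the risk of conversion to open surgery, which is a surgical judgement.
- Criterion 18 is open-ended.
- The assessments that Section 7.2 names as reserved for blinded staff are study endpoints, adverse events and surgical-site examinations. It does not name eligibility or the IWRS entry.

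If entry were shaped by a guessed arm, patients with lower expected pain could be steered towards one treatment. Neither patient blinding nor the MMRM would remove that.

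**Working it through.** The plan gives no predictability figure, so there is none to reproduce.

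**Inputs.** Block size 4, 1:1 ratio, sex as the only named stratum, IWRS (Section 11.3); 5 to 25 sites (Section 6.1); 132 per arm, 90% power, 5% type I error (Section 11.2). Site shares, the sex split and random arrival order are assumptions.

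**1. One observer sees a whole sex stratum** (blocks issued by site, or one site filling a stratum alone). There are six equally likely blocks: AABB, ABAB, ABBA, BAAB, BABA, BBAA. The best guess is the arm with more places left.

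| Position in block | Best guess correct | Certain |
|---|---|---|
| 1 | 1/2 | 0 |
| 2 | 2/3 | 0 |
| 3 | 1/3 × 1 + 2/3 × 1/2 = 2/3 | 1/3 |
| 4 | 1 | 1 |

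- Correct: (1/2 + 2/3 + 2/3 + 1)/4 = 17/24 = 70.8%.
- Certain: (1/3 + 1)/4 = 1/3.
- Incomplete blocks, assuming 50% to 80% female: about 24% to 27% certain at an 11-patient site (264/25), and about 31% to 33% at a 53-patient site (0.20 × 264 = 52.8).

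**2. List shared across sites within sex.** The site sees only its own patients and does not know where it stands in a block. Simulation with an observer who updates optimally after each own-site patient gives:

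| Site share of the list | Best guess correct | Certain |
|---|---|---|
| 50% | 58.9% | 0 |
| 20% | 54.4% | 0 |
| 10% | 52.3% | 0 |
| 4% | 51.0% | 0 |

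**3. Block sizes drawn at random from 4, 6 and 8**, with the set known to the observer:

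- Whole stratum seen: correct about 68% (from 70.8%), certain about 2% (from 33.3%).
- 20% share: correct 53.8% to 53.9% across simulations (from 54.4%), none certain in either case.

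**4. What this could do to the estimate (illustration only).** Let *g* be the difference in mean pain, in SD, between patients entered under one guess and under the other, and *p* the proportion guessed correctly. The false treatment difference is *g*(2*p* − 1). Its shift in z is that value divided by √(2/132), that is, multiplied by √66 = 8.12. With *g* = 0.4 SD (assumed) and all 264 patients affected:

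| Case | *p* | False difference (SD) | Two-sided type I error |
|---|---|---|---|
| Whole stratum seen, fixed 4 | 0.708 | 0.166 | 27% |
| Whole stratum seen, varying | 0.682 | 0.146 | 22% |
| 20% share, fixed 4 | 0.544 | 0.035 | 5.9% |
| 20% share, varying | 0.539 | 0.031 | 5.7% |

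With *g* = 0.2 SD, the fixed-4 type I errors are about 10% and 5.2%. For scale, the sizing implies an effect of 3.2415 × √(2/132) = 0.40 SD (back-calculated, as the plan's value is redacted).

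**The case against.** A reader might infer that a third of this trial's assignments are known in advance, or that the type I error is 27%. The documents do not support either.

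- **List structure.** The one-third and 71% figures need blocks issued by site, or one site alone in a stratum. No visible text says blocks are issued by site. Sex is the only named stratum and an IWRS assigns, so the literal reading is a shared list, on which nothing is certain and a site with a 20% share gains about 4 points over chance.
- **The 27%.** It needs within-site blocks, all 264 patients affected, and a 0.4 SD gap between the two guessed groups, all at once.
- **Dominant or early sites.** The sponsor review near 20% of 264 bears on this, though it is not a cap. That sites open to Part 2 at different times is an inference: Section 11.2 says only that the final size of Part 1 is "determined by the readiness of sites to enroll subjects under IRB-approved Part 2".
- **Replacement.** About 4% of patients are expected not to be dosed, and they are to be replaced. This breaks the tally, and the calculations above leave it out.
- **Route to selection.** Nothing states that un-blinded staff make entry decisions. Site Blinding Plans, which are not supplied, assign roles, and the Section 7.2 sign-off on protocol evaluations could be read to cover eligibility.
- **Small gain.** Varying the block size nearly removes certainty but hardly changes the average guess, and the bias in step 4 depends only on the average guess.

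All of this stands as to size. It does not give a reason to print the block size in a document that sites hold, and the documents do not exclude the within-site case.

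**Conclusion.** The weakness is real and its likely effect is small. The protocol discloses a single block length to sites where several people are un-blinded, and nothing visible separates those people from eligibility or entry. On the literal reading of a shared list, their advantage is about 1 to 4 points over chance for site shares of 4% to 20%. Only if blocks are issued by site, or while one site fills a sex stratum alone, does it reach 71% correct with one third certain. These figures rest on assumed site shares, random arrival order and full memory of earlier own-site assignments. This is a case for a low-cost improvement. It is not evidence that the primary comparison is materially biased.

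**What to change.** In Section 11.3, for Part 2 or the unissued part of its list, replace the description of permuted blocks of size 4 with: *randomly permuted blocks of randomly varying size, stratified by sex, generated centrally and not issued by site*. Keep the block sizes only in the restricted IWRS specification. The 1:1 ratio, the sex strata and the IWRS stay as they are.

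The clause on not issuing blocks by site matters most, because it settles the question on which the size of the problem turns. Varying the sizes is the second safeguard: in the within-site case certain assignments fall from 33% to about 2% and correct guesses from 71% to 68%. On a shared list the gain is under 1 point at a 20% share.

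The cost is one amended sentence and regeneration of the unissued list. If Part 2 is under way, open blocks must be handled and the IWRS replacement algorithm checked again. With blocks of up to 8, the final imbalance could reach 4 rather than 2 patients per sex stratum, a negligible loss of precision with 264 patients. No extra patients or procedures are needed.

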#### 11.4 Definition of Analysis Population

**ITT Population:** The ITT population will consist of all randomized patients in both Part 1 and Part 2 independent of their exposure to test drug or completion of surgery. However, the primary efficacy analysis will include only Part 2 data.

**Safety Population:** The Safety population will consist of all subjects in both Part 1 and Part 2 who received any amount of test drug. The Safety population will be used for all safety analyses.

**Modified Intention-to-Treat (mITT) Population:** All randomized patients in both Part 1 and Part 2 who receive any test drug. However, the primary efficacy analysis will include only Part 2 data.

All efficacy endpoints will be analyzed using the mITT set.

